18.2 Monitoring, Quality Control and Assurance

The trial will be managed through the Chief Investigator, [name] and the Newcastle Clinical Trials Unit (NCTU). The MUSTARDD-PD Trial Management Group (TMG) will include: [name], together with the Trial Manager (Senior Manager and Manager dedicated to study), the Trial Statistician, Data Manager, Project Secretary and a representative from the DeNDRoN UK coordinating centre. *Ad hoc* members will comprise representatives of the Sponsor Organisation's R&D Department, University Finance (Grants and Contracts) and the Institute of Ageing and Health, Newcastle University.

The Principal Investigators will be responsible for the day-to-day study conduct at each site.

NCTU, primarily through the MUSTARDD-PD Trials Manager, will provide day-to-day support for the sites and provide training via Investigator meetings, site initiation visits/teleconferences and routine monitoring visits.

Quality control will be maintained through adherence to NCTU-wide SOPs, MUSTARDD-PD study-specific SOPs, the study protocol, the principles of GCP, research governance regulations and clinical trial regulations.

An independent Data Monitoring and Ethics Committee (DMEC) will monitor efficacy and safety endpoints. Only the DMEC will have access to un-blinded study data. The committee will convene on a 6-monthly basis. Other than the initial meeting, these meetings may be held by teleconference. At the first meeting, the DMEC will discuss and advise on the inclusion of an interim analysis and possible adoption of a formal stopping rule for efficacy or safety. The membership of the MUSTARDD-PD DMEC is listed in Appendix K. The DMEC will agree its terms of reference and mode of operation at its first meeting, drawing on the DAMOCLES charter.

A Trial Steering Committee (TSC) will provide overall supervision of the trial. The membership of the TSC is listed in Appendix L. The committee will meet every 6 months for the duration of the trial. The TSC will agree its terms of reference and mode of operation at the first meeting.

Monitoring of study conduct and data collected will be performed by a combination of central review and site monitoring visits to ensure that the study is conducted in accordance with GCP. Study site monitoring will be undertaken by the trial manager. The main areas of focus will include consent, serious adverse events, recording of primary outcome measures, essential documents in study files, and drug accountability and management.

Site monitoring will be determined following a full risk assessment of the study and production of the study Monitoring Plan. It is anticipated that this will include:

- All original consent forms, reviewed as part of the study file.
- The presence of a copy of the consent form in the patient hospital notes. This will be confirmed for a selected number of patients as determined by the study risk assessment and Monitoring Plan.
- All original consent forms, compared against the study Participant Identification List and the Study Personnel Delegation Log.
- All reported serious adverse events, verified against treatment notes/medical records (source data verification).
- A check of the presence of all essential documents in the study file.
- Source data verification of primary endpoint data and eligibility data will be undertaken for a random sample of participants entered in the study. The numbers will be determined by the study risk assessment and Monitoring Plan.
- Drug accountability and management checked at site level.

Central monitoring will include:

- All applications for study authorisations or submissions of progress/safety reports will be reviewed for accuracy and completeness, prior to submission.
- All documentation essential for study initiation reviewed prior to site authorisation.
- Statistical monitoring of data, including outliers and inconsistencies.

All monitoring findings will be reported and followed up with the appropriate persons in a timely manner.

The study may be subject to inspection and audit by The Newcastle upon Tyne Hospitals NHS Foundation Trust under their remit as sponsor, and other regulatory bodies (eg MHRA) to ensure adherence to GCP. The investigator(s) / institutions will permit trial-related monitoring, audits, REC review and regulatory inspection(s), providing direct access to source data/documents.

19. Pharmacovigilance

19.1 Definitions

Adverse event (AE): Any untoward medical occurrence which does not necessarily have a causal relationship with the treatment. "Treatment" includes all investigational agents (including comparative agents) administered during the course of the study. Medical conditions/diseases present before starting study treatment are only considered adverse events if they worsen after starting study treatment.

Adverse Reaction (AR): Any untoward or unintended responses to an Investigational Medicinal Product (IMP) related to any dose administered - All AEs judged by either the reporting investigator or the sponsor as having reasonable causal relationship to a medicinal product qualify as adverse reactions. The expression "reasonable causal relationship" means to convey in general that there is evidence or argument to suggest a causal relationship.

Causality:

The assignment of the causality should be made by the investigator responsible for the care of the participant using the definitions in the table below. All adverse events judged as having a reasonable suspected causal relationship to the IMP(s) (i.e. definitely, probably or possibly related) are considered to be adverse reactions. If any doubt about the causality exists, the local Principal Investigator should inform the Chief Investigator. In the case of discrepant views on causality between the Principal Investigator and others, all parties will discuss the case. In the event that no agreement is made, the MHRA, main REC and other bodies will be informed of both points of view.

Relationship	Description					
Unrelated	There is no evidence of any causal relationship					
Unlikely	There is little evidence to suggest there is a causal relationship (e.g. the event did not occur within a reasonable time after administration of the trial medication). There is another reasonable explanation for the event (e.g. the participant's clinical condition, other concomitant treatment).					
Possible	There is some evidence to suggest a causal relationship (e.g. because the event occurs within a reasonable time after administration of the trial medication). However, the influence of other factors may have contributed to the event (e.g. the participant's clinical condition, other concomitant treatments).					
Probable	There is evidence to suggest a causal relationship and the influence of other factors is unlikely.					
Definitely	There is clear evidence to suggest a causal relationship and other possible contributing factors can be ruled out.					
Not assessable	There is insufficient or incomplete evidence to make a clinical judgement of the causal relationship.					

Serious Adverse Event (SAE) or Serious Adverse Reaction (SAR): any untoward medical occurrence or effect that, at any dose:

- Results in death
- Is life-threatening refers to an event in which the subject was at risk of death at the time of the event; does not refer to an event which hypothetically might have caused death if it were more severe
- Requires hospitalisation, or prolongation of existing inpatients' hospitalisation
- Results in persistent or significant disability or incapacity
- Results in a congenital anomaly or birth defect.

Medical judgement should be exercised in deciding whether an AE/AR is serious in other situations. Important AE/ARs that are not immediately life-threatening or do not result in death or hospitalisation but may jeopardise the subject or may require intervention to prevent one of the other outcomes listed in the definition above, should also be considered serious.

Suspected, Unexpected Serious Adverse Reaction (SUSAR): an adverse reaction that is both unexpected and serious. An adverse reaction is 'unexpected' if its nature or severity is not consistent with the applicable product information (see Appendix A1 and 2).

Severity (intensity) of Adverse Events and Adverse Reactions

Severity of all AEs and ARs will be graded on a three-point scale of intensity (mild, moderate, severe):

Mild: Discomfort is noticed, but there is no disruption of normal daily activities. **Moderate:** Discomfort is sufficient to reduce or affect normal daily activities. **Severe:** Discomfort is incapacitating, with inability to work or to perform normal daily activities.

An AE or AR may be severe but not serious.

19.2 Expected Adverse Reactions

Most adverse events and adverse drug reactions that occur in this study, whether they are serious or not, will be expected treatment-related toxicities due to the drugs used in this study. These include diarrhoea, muscle cramps, tiredness, sleeplessness and nausea. These problems can occur in up to 10% of people but are usually mild in nature. For a full list of expected undesirable effects of donepezil hydrochloride, please refer to the Summary of Product Characteristics (Appendix A1 and 2).

19.3 Protocol Specifications

For purposes of this protocol

- All non-serious adverse reactions will be recorded at visits 3-7.
- Any serious adverse events will be recorded throughout the duration of the trial until 2 weeks after the trial medication is stopped.
- Serious adverse events exclude any pre-planned hospitalisations not associated with clinical deterioration.
- Serious adverse events exclude routine treatment or monitoring of the studied indication, not associated with any deterioration in condition.
- Serious adverse events exclude elective or scheduled treatment for pre-existing conditions that did not worsen during the study.

19.4 Recording and Reporting Serious Adverse Events or Reactions:

All adverse events should be reported. Depending on the nature of the event, the reporting procedures below should be followed. Any questions concerning adverse event reporting should be directed to the Chief Investigator or MUSTARDD-PD Trial Manager in the first instance. Figure 1 summarises the reporting procedures.

Adverse Event (including Adverse Reaction): All non-serious adverse events / reactions during drug treatment will be reported on the study CRF and sent to Newcastle Clinical Trials Unit within 2 weeks of the form being due. Severity of AEs will be graded on a three-point scale (mild, moderate, or severe – see above). Relation of the AE to the treatment should be assessed by the investigator at site. The individual investigator at each site will be responsible for managing all adverse events / reactions according to local protocols as the study drug is licensed for use in other indications.

Serious Adverse Event / Reaction (SAE/SAR, including SUSARs): All SAEs, SARs and SUSARs during drug treatment will be reported to the Chief Investigator within 24 hours of learning of their occurrence. The initial report can be made by telephone, fax or e-mail. In the case of incomplete information at the time of initial reporting, all appropriate information should be provided as follow-up as soon as this becomes available. Relationship of the SAE to the treatment should be assessed by the investigator at site, as should the expected or unexpected nature of any serious adverse reactions.

The MHRA and main REC will be notified of all SUSARs occurring during the study according to the following timelines; fatal and life-threatening within 7 days of notification and non-life threatening within 15 days. All investigators will be informed of all SUSARs occurring throughout the study on a case-by-case basis.

The Chief Investigator will ensure that the Newcastle upon Tyne Hospitals NHS Foundation Trust is notified of any SUSARs in accordance with local Trust policy.

Local investigators should report any SUSARs and / or SAEs as required by their Local Research Ethics Committee and/or Research & Development Office.

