Note: Assessments 1-7 must be carried out by an independent rater (that is, an investigator who is unaware of the outcome of the other assessments to be performed at this visit, such as recording of adverse events, which could potentially un-blind the assessor). The participant should be requested not to discuss possible adverse events or interim problems with this rater prior to their assessments being performed.

Note: Ensure an adequate rest break is provided during the visit along with refreshments for the patient and the spokesperson.

Visit 7: End of study - 104 weeks (± 7 days)

The following procedures and assessments will be carried out at this visit:

- 1. Mattis DRS-2
- 2. NPI-10 (administered to caregiver/informant)
- 3. BADLS (administered to caregiver/informant)
- 4. Modified ADCS-CGIC interview and scoring
- 5. Montreal Cognitive Assessment (MoCA)
- 6. Parkinson's Disease Cognitive Rating Scale (PD-CRS)
- 7. SCales for Outcomes of PArkinson's disease-cognition (SCOPA-cog) (administered to patient)
- 8. EQ-5D
- 9. DEMQOL and DEMQOL-proxy (latter administered to caregiver/informant)
- 10. Scale of Quality of Life of Caregivers (administered to caregiver/informant)
- 11. UPDRS
- 12. Client Service Receipt Inventory (assessing service use over preceding 6 months) (administered to caregiver/informant)
- 13. Activities-Specific Balance Confidence Scale (ABC)
- 14. Review any adverse events
- 15. Haematological and biochemical tests, as outlined above for visit 5
- 16. Check concomitant medications
- 17. Check study medication returned.

Note: Assessments 1-7 must be carried out by an independent rater (that is, an investigator who is unaware of the outcome of the other assessments to be performed at this visit, such as recording of adverse events, which could potentially un-blind the assessor). The participant should be requested not to discuss possible adverse events or interim problems with this rater prior to their assessments being performed.

Note: Ensure an adequate rest break is provided during the visit along with refreshments for the patient and the spokesperson.

Note: If a participant withdraws prematurely from the study, the end of study visit procedures and assessments should be attempted at the point of withdrawal.

Visit 8: Telephone Call (week 106 ± 2 days)

The purpose of this call is primarily to record any adverse effects that may have occurred in the two weeks after discontinuation of study medication.

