16.1 Statistical Analysis

Analysis will be on the basis of intention to treat. The main statistical challenge in analysing such data is to take into account incomplete data which will be due to a number of factors including the occurrence of side effects or the death of individual participants. Although approximately 50% of patients are expected to discontinue medication prematurely during the study, the actual loss to follow up at 104 weeks is expected to be around 20%, yielding 80% of the original group providing data on the primary outcome measures at 104 weeks. It is likely that those participants who are lost to follow up during the trial may also be people with a tendency to experience poorer outcomes (in terms of the DRS scores) than those who remain in the study.

It is necessary to take into account any difference in dropout rates and the non-randomness of the drop out when comparing functional status between the two treatment groups. This will be done by jointly modelling "survival in the study" and the repeated measures of functional status simultaneously ³³ using software that has been developed as part of an MRC funded programme of work (Grant G0400615; Statistical methodology for longitudinal studies in clinical research; Williamson PR, Diggle PJ and Henderson R). Time to drop-out will be analysed using a Cox proportion hazards model incorporating random effects. Functional outcomes will be modelled using mixed models appropriate for repeated measures. A key feature of each of these models is that within each it is possible to fit a latent variable that can be conceptualised as the patient's propensity to experience poor outcomes (both their likelihood to drop out of the study and their likelihood to have poor DRS scores). It is the inclusion of this latent variable that allows us to adjust our estimates of the treatment effect to allow for the different rates of drop out in each group. Both models are estimated simultaneously; parameter estimates are based on maximising the joint likelihood over both the survival and repeated measures data.

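### The protocol's rules on which adverse events are recorded, at which visits and for how long conflict, and on the natural reading SAEs go unrecorded in participants who stop drug early but stay in intention-to-treat follow-up

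*Protocol*

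**What the plan says.** The rules on recording safety events are spread over several sections of the protocol.

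- **19.3, serious events:** "Any serious adverse events will be recorded throughout the duration of the trial until 2 weeks after the trial medication is stopped".
- **19.3, non-serious events:** "All non-serious adverse reactions will be recorded at visits 3-7". Section 19.1 defines a reaction as an event judged to have a reasonable causal relationship to the product.
- **19.4, general rule:** "All adverse events should be reported".
- **19.4, serious events:** "All SAEs, SARs and SUSARs during drug treatment will be reported to the Chief Investigator within 24 hours of learning of their occurrence".
- **19.4, non-serious events:** it names both events and reactions, and has "reactions during drug treatment will be reported on the study CRF".
- **19.4, SUSAR paragraph:** the regulator and main ethics committee are told of every SUSAR that occurs during the study, with no on-drug condition.
- **15.1, Visit 8 (fixed at week 106, with a two-day window):** "The purpose of this call is primarily to record any adverse effects that may have occurred in the two weeks after discontinuation of study medication". The schedule in 15.2 marks adverse events at every contact from Visit 3 to Visit 8.

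Section 16.1 expects heavy discontinuation of drug: "Although approximately 50% of patients are expected to discontinue medication prematurely during the study". Sections 16.1 and 16.2 expect only about 20% to be lost by week 104. Section 17.2 keeps those who stop drug on the visit schedule, with their permission, because the intention-to-treat analysis needs them.

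**The concern.** There are two linked problems.

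The first is contradiction. The passages differ on event type, visits and recording window, so sites that follow different sections will collect different safety data.

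The second is fit to the design. Efficacy is followed to week 104 whatever the drug status, but neither 19.3 nor 19.4, read naturally, carries SAE recording to that point for someone who stops early. No contact is tied to an early stopper's own stop date plus two weeks either, because Visit 8 is fixed at week 106.

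At stake is the safety comparison between arms. If one arm stops drug more often, it has less recorded time, and its raw SAE count or proportion falls with no true difference. The Existing Research part of section 7 reports 73% completing treatment on rivastigmine against 82% on placebo in the earlier trial, mainly because of adverse events, so unequal stopping is plausible. No analysis plan can recover events that were never recorded.

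**Working it through.** **The conflicting rules side by side**

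| | 19.3 | 19.4 | 15.1 and 15.2 |
|---|---|---|---|
| Non-serious: what | reactions | events and reactions | any adverse events (Visits 4–7); adverse effects (Visit 8) |
| Non-serious: when | Visits 3–7 | while on drug | Visits 3–8 |
| SAE window | to two weeks after drug stops | while on drug; SUSARs notified onward for the whole study | reviews to week 106, no on-drug condition |

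Within 19.4, sites pass SUSARs to the Chief Investigator only while the participant is on drug, yet the onward notification covers the whole study. The narrower rule cannot feed the wider one.

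**How many are affected**

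Inputs: 500 randomised (16.2), 50% stop drug and 20% are lost by week 104 (16.1, 16.2).

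- If everyone lost is also a stopper: 50% − 20% = 30%, or 150 of 500, are off drug and still followed at week 104.
- If stopping and loss are independent: 0.5 × 0.8 = 40%, or 200 of 500.

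**How much follow-up time lies outside the 19.3 window**

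The protocol gives no figure for this and no timing of stops, so the timing is assumed. Those lost are first counted among the stoppers (the 30% case).

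- *Uniform stopping and loss.* Mean follow-up = 104 × (1 − 0.2/2) = 93.6 weeks. Time more than two weeks after stopping = 0.3 × 102²/(2 × 104) = 15.0 weeks. Share = 15.0/93.6 = **16%**.
- *Constant hazards.* Loss hazard = −ln(0.8)/104. Hazard of stopping while still followed = ln(0.8/0.5)/104. Mean follow-up = 93.2 weeks, of which 75.7 lie within the window. Share = 1 − 75.7/93.2 = **19%**.
- *All stops spread over the first 26 weeks.* Time outside = 0.3 × (26/2 + 76) = 26.7 weeks. Share = 26.7/93.6 = **29%**.

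With 40% to 60% stopping, the range over these three patterns is about 11% to 38%.

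In the 40% case with uniform stopping, time outside = (0.5/104) × ∫ from 2 to 104 of (t − 2)(1 − 0.2t/104) dt = 21.6 weeks, and 21.6/93.6 = 23%. The 16–19% is therefore the lower end of what the protocol's own percentages allow when stops are spread over the trial.

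**What a difference between arms would do**

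Take the nine-point gap of the cited trial (82 − 73), centre it on 50%, and keep uniform stopping with 20% loss in each arm. The 102²/(2 × 104) above is 50.02 weeks.

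- 54.5% stopping: 93.6 − 0.345 × 50.02 = 76.3 recorded weeks.
- 45.5% stopping: 93.6 − 0.255 × 50.02 = 80.8 recorded weeks.
- Ratio = 76.3/80.8 = 0.944, so recorded time is about 6% shorter in the arm that stops more.

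With a constant SAE rate and no true effect, the expected raw SAE count would be about 6% lower in that arm. This is an illustration: the gap comes from another drug over 24 weeks.

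**The case against.** The strongest reply is that truncation is only one reading. The 19.3 sentence speaks of the whole duration of the trial, and Visit 8 uses the same two-week interval at week 106. Together they could mean week 106 for everyone. The unconditional reviews at Visits 4 to 7, the schedule's marks to Visit 8 and the SUSAR paragraph all support that. This stands as evidence of ambiguity. It does not settle the matter, because 19.4 ties reporting to time on drug and the 19.3 sentence ends at the stop of medication. The reporting figure cited in 19.4 is not available here and might help.

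It is also fair that recording for a fixed period after last dose is a common convention and not wrong in itself, and that the safety analysis may be set out in an analysis plan not shown. Rates per recorded person-time would remove the time imbalance. They would not restore the off-drug events.

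A reader might infer more than the documents support:

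- *That half of participants stop and stay.* Half are expected to stop; about 30–40% would be off drug and still followed at week 104.
- *That everything at week 106 is lost.* A participant who stops drug at week 104 has SAEs recorded to week 106 under 19.3. Only non-serious events at Visit 8 fall outside that section.
- *That events judged unrelated are not collected at all.* The visit lists review any adverse event, 19.4 covers events as well as reactions, and the causality table has unrelated and unlikely categories. The wording of 19.3 conflicts with this, but a loss of data is not shown.
- *That the primary model cannot learn of deaths.* It models time to drop-out, and 16.1 names death as a cause of incomplete data. A death would normally surface as drop-out without an SAE form.

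**Conclusion.** The conflict between 19.3, 19.4, Visit 8, the schedule and the SUSAR paragraph needs no assumption, and it should be resolved. On the natural reading of 19.3 and 19.4, SAEs that occur more than two weeks after an early stop fall outside recording although the participant is still followed.

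The size rests on the protocol's 50% stopping and 20% loss and on an assumed timing of stops: in the 30% case, about 16–19% of follow-up time with uniform or constant-hazard stopping, and up to about 29% if all stops come within 26 weeks. Any bias between arms also needs unequal stopping and a summary by raw counts or proportions; neither is established for this trial.

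The truncation is partial: visit reviews and monthly falls diaries continue for those who attend, though the reviews themselves conflict with the narrower windows. The point concerns the safety comparison; the sample size and primary efficacy test are unaffected.

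**What to change.** Reconcile 15.1 (Visit 8), 15.2, 19.3 and 19.4 into one event definition and one recording period:

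- In 19.3, record all SAEs and deaths from randomisation to week 106 for every participant still in follow-up, on or off drug.
- In 19.3, change the non-serious item from reactions to events, and from Visits 3–7 to Visits 3–8.
- In 19.4, remove the on-drug limit on SAE and SUSAR reporting, so that it matches 19.3 and the SUSAR paragraph.

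Both an on-treatment summary (last dose plus two weeks) and an intention-to-treat summary can then be produced from the same record.

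The cost is amendment wording and some extra SAE forms for participants who are already asked to attend. No visits are added and the sample size does not change.
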